23. APPENDIX V. ADDITIONAL RESTRICTED SUBSTANCES

CYP3A4 Inducer	CYP3A4 Inhibitor
Carbamazepine	Amiodarone
Phenobarbital	Cimetidine
Phenytoin	Clarithromycin
Pioglitazone	Diltiazem
Rifabutin	Erythromycin
Rifampin	Fluvoxamine
St John's Wort	Grapefruit and grapefruit juice
	Indinavir
	Itraconazole
	Ketoconazole
	Mibefradil
	Nefazodone
	Nelfinavir
	Ritonavir
	Verapamil
	Troleandomycin

This is not an all-inclusive list of restricted enzyme inducers and inhibitors.

24. APPENDIX VI: BODY MASS INDEX DETERMINATION

Body mass index (BMI) will be calculated by measuring the subject's height and weight (both determined without subject wearing shoes) and using these measurements (in centimeters and kilograms) in the following formulae.

Formula:

$$BMI = weight (kg) \div [height (cm) \div 100]^2$$

The entries in the following table list the BMI values for subjects of a given height and weight. Please note this table is not inclusive of all possible height and weight combinations.

Body Mass Index (BMI) in kg/m² According to Height and Weight

BMI	Heig	leight																					
	Cm	142.2	144.8	147.3	149.9	152.4	154.9	157.5	160.0	162.2	165.1	167.6	170.2	172.7	175.3	177.8	180.3	182.9	185.4	188.0	190.5	193.0	195.6
Weight	t																						
kg																							
40.9		20	20	19	18	18	17	17	16	15	15	15	14	14	13	13	13	12	12	12	11	11	11
43.2		21	21	20	19	19	18	17	17	16	16	15	15	14	14	13	13	13	13	12	12	12	11
45.4		21	22	21	20	20	19	18	18	17	17	16	16	15	15	14	14	14	13	13	13	12	12
47.6		24	23	22	21	21	20	19	19	18	18	17	16	16	16	15	15	14	14	14	13	13	12
49.9		25	24	23	22	22	21	20	20	19	18	18	17	17	16	16	15	15	15	14	14	13	13
52.3		26	25	24	23	23	22	21	20	20	19	19	18	18	17	17	16	16	15	15	14	14	14
54.4		27	26	25	24	23	23	22	21	21	20	19	19	18	18	17	17	16	16	15	15	15	14
56.8		28	27	26	25	24	24	23	22	22	21	20	20	19	18	18	17	17	17	16	16	15	15
59.0		29	28	27	26	25	25	24	23	22	22	21	20	20	19	19	18	18	17	17	16	16	15
61.4		30	29	28	27	26	26	25	24	23	23	22	21	21	20	19	19	18	18	17	17	16	16
63.5		31	30	29	28	27	27	26	25	24	23	23	22	21	21	20	20	19	19	18	18	17	17
65.9		33	31	30	29	28	27	27	26	25	24	23	23	22	21	21	20	20	19	19	18	18	17
68.0		34	33	31	30	29	28	27	27	26	25	24	24	23	22	22	21	20	20	19	19	18 19	18
70.5 72.6		35	35	34	31	30	29 30	28 29	28 28	27 28	26 27	25 26	24 25	24	23	23	22	21	20	20	19 20	20	18
75.0		37	36	35	33	32	31	30	29	28	28	27	26	25	24	24	23	22	22	21	21	20	20
77.1		38	37	36	34	33	32	31	30	29	28	27	27	26	25	24	24	23	22	22	21	21	20
79.5		39	38	37	35	34	33	32	31	30	29	28	27	27	26	25	24	24	23	23	22	21	21
81.6		40	39	38	36	35	34	33	32	31	30	29	28	27	27	26	25	24	24	23	23	22	21
84.1		42	40	39	37	36	35	34	33	32	31	30	29	28	27	27	26	25	24	24	23	23	22
86.2		43	41	40	38	37	36	35	34	33	32	31	30	29	28	27	27	26	25	24	24	23	23
88.6		44	42	41	39	38	37	36	35	34	33	32	31	30	29	28	27	27	26	25	24	24	23
90.7		45	43	42	40	39	38	37	36	34	33	32	31	30	30	29	28	27	26	26	25	24	24
93.2		46	44	43	41	40	39	38	36	35	34	33	32	31	30	29	29	28	27	26	26	25	24
95.3		47	45	44	43	41	40	38	37	36	35	34	33	32	31	30	29	29	28	27	26	26	25
97.7		48	47	45	44	42	41	39	38	37	36	35	34	33	32	31	30	29	28	28	27	26	26
99.8		49	48	46	45	43	42	40	39	38	37	36	35	34	33	32	31	30	29	28	28	27	26
102.3		51	49	47	46	44	43	41	40	39	38	36	35	34	33	32	31	31	30	29	28	27	27
104.3		52	50	48	47	45	44	42	41	40	38	37	36	35	34	33	32	31	30	30	29	28	27
106.8		53	51	49	48	46	44	43	42	40	39	38	37	36	35	34	33	32	31	30	29	29	28
109.8		54	52	50	49	47	45	44	43	41	40	39	38	37	36	35	34	33	32	31	30	29	29
111.4		55	53	51	50	48	46	45	43	42	41	40	38	37	36	35	34	33	32	32	31	30	29

## 1. ABBREVIATIONS

Abbreviation	Description
ACS	Abnormal, clinically significant
AE	Adverse event
Ae	Amount of drug excreted in urine
ALT	Alanine aminotransferase
ANCS	Abnormal, not clinically significant
AST	Aspartate aminotransferase
AUC	Area under the serum concentration-time curve
BLQ	Below Limit of Quantification
BMI	Body mass index
CI	Confidence interval
CL/F	Apparent clearance after extravascular administration
C last	The last postdose quantifiable serum concentration
CLR	Renal clearance
C max	Maximum observed serum concentration
CRF	Case report form (or electronic case report form)
C-SSRS	Columbia-suicide severity rating scale
CV	Coefficient of variation
ECG	Electrocardiogram
eCRF	Electronic case report form
fe	Fraction of drug excreted in urine
GCV	Geometric coefficient of variation
GM	Geometric mean
IPD	Important protocol deviation
ISF	Inform consent
ISAF	Injectable safety population
MedDRA	Medical dictionary for regulatory activities
OSAF	Oral safety population
MR	Metabolite to parent compound ratio
NCS	Not clinically significant
PANSS	Positive and Negative Syndrome Scale
PK	Pharmacokinetic
PD	Pharmacodynamic
PR	Time Between P Wave and QRS In Electrocardiography
PT	Preferred term
PTE	Pretreatment event
QRS	Electrocardiographic wave (complex or interval)
QTcF	QT interval with Fridericia's correction method
SAE	Serious adverse event
SAP	Statistical analysis plan
SD	Standard deviation

Document:

Author:

Version Number:  
 Version Date:

Final Draft  
 11APR2019

Template No: CS\_TP\_BS016 Revision 4  
 Effective Date: 01Apr2016

Reference: CS\_WI\_BS005

Abbreviation	Description
SOC	System organ class
SOP	Standard operating procedure
SRT	Safety review team
$t_{1/2}$	Terminal half-life
$t_{last}$	Time of the last postdose quantifiable serum concentration
$t_{max}$	Time to reach $C_{max}$
ULN	Upper limit of normal
ULQ	Upper limit of quantification
US	United states
$V_z/F$	Apparent volume of distribution during the terminal phase after extravascular administration
WHODRUG	World Health Organization drug
$\lambda_z$	Terminal rate constant

## 2. INTRODUCTION

This document describes the rules and conventions to be used in the presentation and analysis of safety and pharmacokinetics (PK) data for Protocol D1052024. It describes the data to be summarized and analyzed, including specifics of the statistical analyses to be performed.

This statistical analysis plan (SAP) is based on protocol version 1.0 dated 26 March 2018 and protocol amendment version 2.0, dated 13 June 2018.

## 3. STUDY OBJECTIVES

### 3.1. SAFETY OBJECTIVE

The safety objective is

To assess safety, tolerability, and pharmacokinetics (PK) of a single dose of lurasidone injectable suspension in subjects with schizophrenia.

### 3.2. PHARMACOKINETIC AND PHARMACODYNAMIC OBJECTIVES

Pharmacokinetic and Pharmacodynamic (PD) objectives are:

---

Document:

Author:

Version Number:  
 Version Date:

Final Draft  
 11APR2019

Template No: CS\_TP\_BS016 Revision 4  
 Effective Date: 01Apr2016

Reference: CS\_WI\_BS005

To assess the PK for the metabolites of lurasidone in serum (ID-14283, ID-14326, ID-11614, ID-20219 and ID-20220) and in urine (ID-14283, ID-14326, and ID-11614) after a single dose of lurasidone injectable suspension.

To assess Positive and Negative Syndrome Scale (PANSS) in subjects with schizophrenia after a single dose of lurasidone injectable suspension.

### **3.3. STUDY ENDPOINTS**

#### **3.3.1. SAFETY ENDPOINTS**

Incidence of AEs, serious adverse events (SAEs), and AEs leading to study discontinuation

Incidence of injection site-related reactions, including injection site pain, injection site erythema, injection site induration, injection site ulcer, injection site granuloma and injection site swelling

Observed values and changes from baseline in clinical laboratory tests (hematology, serum chemistry, urinalysis, coagulation, and liver function), vital signs (respiratory rate, body temperature, supine blood pressure, and pulse), orthostatic effects (based on blood pressure and pulse rate), and 12-lead electrocardiograms (ECGs) parameters

Incidence and severity of subjects with suicidal ideation or suicidal behavior using the Columbia Suicide Severity Rating Scale (C-SSRS)

#### **3.3.2. PHARMACOKINETIC ENDPOINTS**

Pharmacokinetic parameters for lurasidone after Lurasidone injectable suspension administration

- Serum:  $C_{max}$ ,  $t_{max}$ ,  $C_{last}$ ,  $t_{last}$ ,  $AUC_{0-144}$ ,  $AUC_{0-last}$ ,  $AUC_{0-inf}$ ,  $\lambda_z$ ,  $t_{1/2}$ ,  $CL/F$ , and  $V_z/F$
- Urine:  $Ae_{0-144h}$ ,  $fe_{0-144}$ , and  $CLR$

Pharmacokinetic parameters for metabolites after Lurasidone injectable suspension administration

- Serum:  $C_{max}$ ,  $t_{max}$ ,  $C_{last}$ ,  $t_{last}$ ,  $AUC_{0-144}$ ,  $AUC_{0-last}$ ,  $AUC_{0-inf}$ ,  $\lambda_z$ ,  $t_{1/2}$ , metabolite to parent ratio of  $AUC_{0-inf}$  ( $MR_{AUC0-inf}$ ), and  $C_{max}$  ( $MR_{Cmax}$ ) for ID-14283, ID-14326, ID-11614, ID-20219, and ID-20220
- Urine:  $Ae_{0-144h}$  for ID-14283, ID-14326, and ID-11614

---

Document:

Author:

Version Number:  
Version Date:

Final Draft  
11APR2019

Template No: CS\_TP\_BS016 Revision 4  
Effective Date: 01Apr2016

Reference: CS\_WI\_BS005

### **3.3.3. PHARMACODYNAMIC ENDPOINT**

Change from baseline, and placebo-corrected change from baseline in PANSS total score.

## **4. STUDY DESIGN**

### **4.1. GENERAL DESCRIPTION**

This is a single-center, randomized, double-blind, placebo-controlled, inpatient, single ascending dose (SAD) study designed to evaluate the safety, tolerability, and PK of lurasidone injectable suspension in subjects with schizophrenia. This study will determine the minimum intolerable dose (MID), the maximum tolerated dose (MTD) of lurasidone injectable suspension and characterize the PK profiles of lurasidone metabolites in serum (ID-14283, ID-14326, ID-11614, ID-20219, and ID-20220) and urine (ID-14283, ID-14326, and ID-11614) in this subject population. The potential effects of gender on the PK of lurasidone injectable suspension and its metabolites will also be evaluated when applicable.

Subjects will receive oral lurasidone 80 mg tablets on Day -7 and Day -6 (one dose per day), and be monitored for 5 days to ensure the subject is able to tolerate lurasidone (ie, absence of moderate adverse events). Subjects who tolerate dosing with oral lurasidone 80 mg will be eligible for randomization to receive a single lurasidone injectable suspension or placebo injection on Day 1.

The study is planned to include up to 5 cohorts. A total of 8 subjects (6 active and 2 placebo) will be dosed in each cohort. Lurasidone injectable suspension dosing will be initiated at 30 mg given as an intramuscular (IM) injection. Subsequent cohorts are planned to be dosed at 75, 150, 300, and 450 mg IM. Dose strengths after the first dose level may be modified based on safety assessments and exposure to lurasidone injectable suspension.

All 5 planned dose cohorts may not be used, depending on the dose escalation strategy employed. Additional cohorts may be included in this study, as necessary, and determined following a review of safety and exposure of lurasidone injectable suspension. Planned dose levels may be modified or repeated based on the overall safety profile of the current and/or previous cohorts.

---

Document:

Author:

[figure not shown]
Version Number:  
Version Date:

Final Draft  
11APR2019

Template No: CS\_TP\_BS016 Revision 4  
Effective Date: 01Apr2016

Reference: CS\_WI\_BS005

**Figure 1: Study Schematic**

a Eligible subjects must be washed out/tapered off of their current antipsychotic medications 5 to 6 half-lives prior to Day -8 (may begin as early as Day -19). Subjects are required to be inpatient from Day -12 to Day 15 (for treatment and observation) and Day 29 to Day 33 (for restabilization to previous medications). Subjects may remain inpatient up to Day 33 (at the Investigator's discretion).

b Subjects will receive 2 oral lurasidone 80 mg doses (Days -7 and -6) and be assessed for safety and tolerability for 5 days (Days -5 to -1) and to allow appropriate time to washout of the oral lurasidone dose.

c Randomization occurs on Day 1. Cohort 1 will receive a single lurasidone injectable suspension dose of 30 mg or a single placebo injection dose; thereafter, single lurasidone injectable suspension doses of 75, 150, 300, and 450 mg may be administered (cohorts 2-5).

d Subjects will be monitored for safety after the single lurasidone injectable suspension or placebo injection dose until Day 29. Subjects may be discharged on Day 15 at the Investigator's discretion.

e Subjects will restart prior medications (including antipsychotics) on Day 29 under observation of clinical site staff.

## 4.2. METHOD OF ASSIGNING SUBJECTS TO TREATMENT GROUPS

The treatment schedule will be generated by a non-study biostatistician.

For each cohort, the randomization number will be sequentially assigned as subjects qualify for the study. Once 8 subjects per cohort are dosed, alternate subjects who are not needed to complete enrollment of a cohort will be discharged following reintroduction of their prior medication if they are clinically stable (in the Investigator's opinion).

Once a randomization number has been assigned, it cannot be reused.

Prior to dosing, all eligible subjects will be given a randomization number that assigns them to one of the two treatments. Randomization numbers will be assigned sequentially in the order the subject became eligible to participate in the study. The treatment schedule, a list consisting of the

---

Document:

Author:

Version Number:  
 Version Date:

Final Draft  
 11APR2019

Template No: CS\_TP\_BS016 Revision 4  
 Effective Date: 01Apr2016

Reference: CS\_WI\_BS005

randomization numbers and their corresponding treatment assignment will be generated according to appropriate standard operating procedure(s).

Subjects will receive single oral lurasidone 80 mg doses on Days -7 and -6 and be monitored for 5 days to ensure the subject is able to tolerate lurasidone (i.e., absence of moderate adverse events). Subjects who tolerate dosing with oral lurasidone 80 mg will be eligible for randomization on Day 1.

For Cohort 1, a sentinel group of 2 subjects will be dosed in a 1:1 ratio (lurasidone injection: placebo). A 7-day clinical assessment of safety and tolerability for the sentinel subjects will be made by the Investigator (including AEs, vital signs, and other clinically relevant findings), the remaining 6 subjects will be randomized in a 5:1 ratio (active: placebo). A sentinel group may not be required for future dose cohorts.

If less than 6 subjects in a cohort complete through Day 29, additional subjects will be enrolled and randomized in a 1:1 ratio (active: placebo) until at least 6 subjects have completed the cohort. If additional subjects need to be enrolled in a cohort, up to 6 additional randomization numbers will be provided in a 1:1 ratio.

## 4.3. BLINDING

All study drug injectable (active or placebo) will be dispensed according to the randomization schedule supplied by the Sponsor or its representative, using a method that will assure that subjects and blinded study site personnel remain blinded to the treatment (ie, active or placebo) being administered.

Provided doses will be clearly labelled with a unique subject identifier and verified during preparation and at the time of administration to mitigate any possibility of dosing/randomization error

During the conduct of the cohorts, in order to maintain the blind during the time of study drug administration, up until a safety review of AEs and other safety data for a cohort is conducted, an unblinded clinical site pharmacist/nurse will dispense study drug in a manner that will protect the blind upon administration

Subjects, Investigator staff, persons performing the assessments, clinical operations personnel, data analysts, and personnel at clinical laboratories will remain blind to the identity of the treatment from the time of randomization until database lock and unblinding, with the exception of the documented safety review process, using the following methods:

- (1) randomization data are kept strictly confidential (eg, sealed envelopes kept in a locked filing cabinet or placed in a safe) until the time of unblinding, and will not be accessible by anyone else involved in the study with the following exceptions:

---

Document:

Author:

Version Number:  
Version Date:

Final Draft  
11APR2019

Template No: CS\_TP\_BS016 Revision 4  
Effective Date: 01Apr2016

Reference: CS\_WI\_BS005

- bioanalytical lab personnel involved in the analysis of PK samples
- safety data review team members involved in regular review of safety data when it is determined that data need to be unblinded

(2) the identity of the treatments will be concealed by the use of study drugs that are all identical in packaging, labeling, schedule of administration, administration, and appearance;

(3) subjects will be dosed by an unblinded site staff member who is not part of the study team and will not conduct any other study related procedures. Preliminary PK concentration data transfer from the bioanalytical lab to the Sponsor's bioanalytical manager and from the Sponsor's bioanalytical manager to the PK scientist (for PK analysis) for each cohort safety review can only be handled with dummy IDs for study subjects. Final PK concentration data transfer can only be performed after the clinical database lock.

Treatment assignments for a particular cohort may be unblinded during a safety review meeting but only after a blinded review of the safety data has been completed.

Potentially unblinding laboratory results (prolactin) will be reviewed by an unblinded medical monitor and be blinded to the Subjects, site staff, and clinical team, as described in the study Medical Monitoring Plan. Results reaching pre-specified criteria will be provided to sponsor and SRT.

## 4.4. DETERMINATION OF SAMPLE SIZE

There will be no formal estimation for the sample size as no previous human PK data are available for lurasidone injectable suspension and the primary endpoints are safety. The sample size of 8 subjects per cohort (6 lurasidone injectable suspension subjects and 2 placebo subjects) is selected based on clinical and practical considerations for a study of this design.

Approximately 70 subjects are planned overall to ensure that up to 40 subjects receive lurasidone injectable suspension or placebo.

## 4.5. CHANGES IN THE CONDUCT OF THE STUDY

There is no change in the conduct of the study.

---

Document:

Author:

Version Number:  
Version Date:

Final Draft  
11APR2019

Template No: CS\_TP\_BS016 Revision 4  
Effective Date: 01Apr2016

Reference: CS\_WI\_BS005

## 4.6. SCHEDULE OF EVENTS

Schedule of events can be found in Table 2 of the protocol.

## 4.7. CHANGES TO ANALYSIS FROM PROTOCOL

There were no changes in the analyses or definitions planned in the protocol.

## 5. PLANNED ANALYSES

The following analyses will be performed for this study:

- Safety Review Team Analyses
- Final Analysis

### 5.1. SAFETY REVIEW TEAM (SRT)

After each cohort, a review of safety data (eg, AE [including potential psychotic symptoms and behavior], vital signs, laboratory data, standard 12-lead ECG, etc.) and lurasidone injectable suspension exposure data, including analyte concentrations and parameters, for all subjects (or at least 5 lurasidone and 1 placebo subjects completed) in each cohort will be performed. Subsequent dosing at the next dose level/cohort will not occur until safety and exposure data (from at least 14 days after the single lurasidone injectable suspension dose) have been evaluated by the Safety Review Team (SRT). The SRT consists of the PI, the Sponsor's Responsible Physician or designee, the Sponsor's Project Medical Lead, the Sponsor's Head of Translational Medicine and Early Development team or designee and the Medical Monitor. The SRT will also determine if sentinel subject dosing is required for study cohorts after Cohort 1.

The decision to proceed to the next dose level/cohort and at what dose level will also be made by the voting members of the SRT, based on a review of the clinical observations, laboratory data, and exposure data, and will require a majority agreement concerning acceptable safety and tolerability of lurasidone injectable suspension. Based on these safety reviews, a more conservative dose escalation may be used that will be less than the planned dose escalation, or subsequent cohorts may repeat a dose level or de-escalate. For each cohort, the SRT will monitor and review AE and exposure data 14 days and 28 days after the injection dose.

---

Treatment assignments for a particular cohort may be unblinded during a safety review meeting, but  
Document:

Author:

Version Number:  
Version Date:

Final Draft  
11APR2019

Template No: CS\_TP\_BS016 Revision 4  
Effective Date: 01Apr2016

Reference: CS\_WI\_BS005

only after a blinded review of the safety data has been completed. PK exposure data will be utilized in the safety review; thus, it will be necessary for the bioanalytical laboratory to be unblinded to treatment assignment for the subjects.

## 5.2. FINAL ANALYSIS

All final, planned analyses identified in this SAP will be performed by IQVIA Biostatistics following Sponsor Authorization of this SAP, Database Lock, Sponsor Authorization of Analysis Sets and Unblinding of Treatment. (Update as required)

# 6. ANALYSIS POPULATIONS

Agreement and authorization of subjects included/ excluded from each analysis set will be conducted prior to the unblinding of the study.

## 6.1. SAFETY [SAF] POPULATIONS

### 6.1.1. ORAL LURASIDONE SAFETY [OSAF] POPULATION

The Oral Lurasidone safety population (OSAF) will contain all subjects who signed the study specific informed consent and received at least one dose of Lurasidone oral tablet.

This population will be used for analysis of concomitant medications and adverse events data along with ISAF population.

### 6.1.2. INJECTABLE SAFETY [ISAF] POPULATION

The Injectable safety population (ISAF) will contain all subjects in the RND set who received injection of the double-blind study drug. Subjects will be classified according to treatment received.

This population will be used for analysis of baseline and safety data.

For summary tables in which data from both ISAF and OSAF populations are summarized, the term Safety Population will be used.

---

Document:

Author:

Version Number:  
Version Date:

Final Draft  
11APR2019

Template No: CS\_TP\_BS016 Revision 4  
Effective Date: 01Apr2016

Reference: CS\_WI\_BS005

## **6.2. PHARMACOKINETIC POPULATION [PK]**

The PK population will include all subjects in the ISAF Population who received lurasidone injectable suspension and have at least one post-dose quantifiable serum or urine lurasidone or metabolite(s) concentration, and had no important protocol deviations or documented reason that a PK profile was unreliable. This population will be used for the analysis of PK data.

## **6.3. PHARMACODYNAMIC POPULATION [PD]**

The PD population will include all subjects in the ISAF Population who have a valid baseline and at least one post baseline PANSS assessment. This population analysis will be used for the analysis of PD data.

# **7. GENERAL CONSIDERATIONS**

## **7.1. REFERENCE START DATE AND STUDY DAY**

Study Day will be calculated from the reference start date and will be used to show start/ stop day of assessments and events.

Reference start date is defined as the day of the injection study drug, (Day 1 is the day of the injection study drug) and will appear in every listing where an assessment date or event date appears.

- If the date of the event is on or after the reference date then:

Study Day = (date of event – reference date) + 1.

- If the date of the event is prior to the reference date then:

Study Day = (date of event – reference date).

In the situation where the event date is partial or missing, Study Day, and any corresponding durations will appear partial or missing in the listings.

## **7.2. BASELINE**

Unless otherwise specified, baseline is defined as the last non-missing measurement taken prior to  
Document:

Author:

Version Number:  
Version Date:

Final Draft  
11APR2019

Template No: CS\_TP\_BS016 Revision 4  
Effective Date: 01Apr2016

Reference: CS\_WI\_BS005

reference start date (including unscheduled assessments). In the case where the last non-missing measurement and the reference start date coincide, that measurement will be considered pre-baseline, but Adverse Events (AEs) and medications commencing on the reference start date will be considered post-baseline.

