- Note: Supine blood pressure and pulse rate should be collected at the same time as 12-lead ECG (when 12-lead ECG is collected for the same timepoint). A window of \pm 10 minutes of scheduled time is allowed. After Cohort 1, timepoints for vital signs may be changed based on observed t_{max} of Lurasidone injectable suspension and its metabolites.
- ^c Standard 12-lead ECGs will be collected at Screening and during the washout/taper period on Days -12 and -8. On Days -7 and -6, standard 12-lead ECGs will be collected predose and 2 hours postdose. Standard 12-lead ECGs will be collected predose and 6, and 12 hours post injection dose on Day 1 and on Days 3, 5, 7, 9, 11, 13, and 15 (time-matched to the predose timepoint on Day 1), and Days 22, 29, and 33 (approximately time-matched to the predose timepoint on Day 1), and Follow-up. A window of ± 15 minutes of scheduled time is allowed for ECGs performed up to and including Day 15. After Cohort 1, these timepoints may be changed based on observed t_{max} of Lurasidone injectable suspension and its metabolites.

^d Hematology, Serum Chemistry, Urinalysis, Lipid Panel, Coagulation Panel, and Thyroid Panel.

- Subjects are to fast ≥ 8 hours prior to blood sample collection for clinical laboratory tests.
- Blood samples will be collected for Hematology and Serum Chemistry at screening, Day -8, Day 1 injection predose, Days 8 and 15 (time-matched to the predose timepoint on Day 1), and Days 22, 29, and 33 (approximately time-matched to the injection predose sample on Day 1), and follow-up. A window of ± 10 minutes is allowed for clinical laboratory test sample collection. Samples will be obtained at the same time that other blood and urine samples are taken whenever possible.
- Blood samples for thyroid panel, coagulation panel, and lipid panel will be collected at Screening, Day -8, Day 1 injection predose, Day 15 (time-matched to the predose timepoint on Day 1), and Day 29 (approximately time-matched to the injection predose sample on Day 1).
- Urinalysis will be collected at screening, Day -8, Day 1 injection predose (time-matched to the predose timepoint on Day 1), Days 8 and 15 (time-matched to the predose timepoint on Day 1), and Days 22, 29, and 33 (approximately time-matched to the injection predose sample on Day 1), and follow-up.

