11.3. Collection and Recording of Adverse Events

All pre-treatment events and AEs must be recorded in the subject's study records/source documents in accordance with the Investigator's normal clinical practice.

All pre-treatment events and AEs must be recorded on the CRF.

Pre-treatment events will be recorded from the time informed consent is provided at Screening until just prior to first lurasidone oral tablet study drug dose at Day -7. AEs will be recorded beginning after first study drug dose administration on Day 1 until the follow-up/study completion visit at Day 61 (\pm 2).

All AEs will be followed until resolution, stabilization of the condition, the event is otherwise explained, or the subject is lost to follow-up.

Each AE is to be evaluated for duration, severity, frequency, seriousness, action taken with the study treatment, outcome, and causal relationship to the study treatment. Definitions for severity, frequency, action taken with the study treatment, outcome, and causal relationship to the study treatment are presented below.

The severity of AE:

- **Mild** Ordinarily transient symptoms that do not influence performance of subject's daily activities. Other treatment is not ordinarily indicated.
- **Moderate** Marked symptoms sufficient to make the subject uncomfortable. Moderate influence on performance of subject's daily activities. Other treatment may be necessary.
- Severe Symptoms cause considerable discomfort. Substantial influence on subject's daily activities. May be unable to continue the study, and other treatment may be necessary.

The frequency of AE:

- Once an isolated episode.
- **Intermittent** occurs on two or more separate occasions.
- **Continuous** does not abate from date of onset to date of resolution.

The outcome of the AE:

- Recovered/Resolved
- Recovering/Resolving
- Not Recovered/Not Resolved
- Recovered/Resolved with Sequelae
- Fatal
- Unknown

The causal relationship of the AE to the study treatment:

Not related

o **Not related** – Improbable temporal relationship and is plausibly related to other drugs or underlying disease.

Related

- o **Possible** occurred in a reasonable time after study drug administration, but could be related to concurrent drugs or underlying disease.
- Probable occurred in a reasonable time after study drug administration, is unlikely to be attributable to concurrent drugs or underlying disease, and there is a plausible mechanism to implicate the study drug.

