## 7.3. RETESTS, UNSCHEDULED VISITS AND EARLY TERMINATION DATA

In general, for by-visit summaries, data recorded at the nominal visit will be presented. Unscheduled measurements collected prior to the first dose of study medication will contribute to the derivation of the baseline value.

Unscheduled measurements collected post baseline will not be included in by-visit summaries but will contribute to the EOS markedly abnormal post-baseline vital signs (MAPVS), markedly abnormal post-baseline laboratory value (MAPLV) and best/ worst case value where required (e.g. shift table).

Early termination (ET) data collected post baseline will be assigned to the next planned visit for that assessment. If the next scheduled visit is more than 14 days, then the ET data will not be included in the by-visit summary tables but will be included in the MAPVS, the MAPLV and the listings. This mapping will be done for all data points used in the PK and safety analyses.

In the case of a retest (same visit number assigned), the latest available measurement for that visit will be used for by-visit summaries.

Listings will include scheduled, unscheduled, retest and early discontinuation data.

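### SAP 7.2 sets baseline by calendar day, so for ECG it does not reliably select the Day 1 predose recording; the overall oral-period ECG row in SAP 18.3 also counts the pre-tablet Day -7 ECG

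*SAP*

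**What the plan says.** SAP 7.1 sets the anchor: "Reference start date is defined as the day of the injection study drug". It is a day, with no time attached. Under SAP 7.2, unless a section specifies otherwise, "baseline is defined as the last non-missing measurement taken prior to" that date. A second sentence covers same-day values: "In the case where the last non-missing measurement and the reference start date coincide, that measurement will be considered pre-baseline". Neither sentence mentions predose or time of day.

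SAP 7.3 uses a different cut-off for unscheduled values: "Unscheduled measurements collected prior to the first dose of study medication will contribute to the derivation of the baseline value".

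The ECG schedule is in footnote c to Protocol Table 2. For the oral phase: "On Days -7 and -6, standard 12-lead ECGs will be collected predose and 2 hours postdose". For the injection day: "Standard 12-lead ECGs will be collected predose and 6, and 12 hours post injection dose on Day 1". Later ECGs fall "on Days 3, 5, 7, 9, 11, 13, and 15 (time-matched to the predose timepoint on Day 1", then on Days 22, 29 and 33 (approximately time-matched) and at follow-up. Neither Table 2 nor Protocol 10.5.3.3 schedules an ECG on Days -5 to -1.

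Protocol 14.3.9 takes the scheduled Day 1 predose value as the general baseline and, if it is missing, the last available value before dosing. SAP 4.7 reports no change to analyses or definitions. SAP 18.4 gives vital signs their own pre-injection baseline; SAP 18.3 gives ECG none.

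For the markedly abnormal ECG categories, SAP 18.3 defines an overall oral period made up of Day -7, Day -6, Day 1 predose, the Baseline record and unscheduled visits. It defines an overall injection period that limits Day 1 to postdose timepoints. Day -7 has no such limit.

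**The concern.** ECG is the measurement most exposed to a date-only rule, because Day 1 has recordings on both sides of the injection. Scheduled Day 1 laboratory tests and PANSS are predose only, so the same-day sentence works for them. Vital signs have their own rule.

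If SAP 7.2 were programmed literally for ECG, changes in QTc, PR, QRS and heart rate would be measured from a post-injection recording, or from one made 2 h after an oral tablet six days earlier. Either would break the protocol's time-matching to Day 1 predose and feed the change-from-baseline categories in SAP 18.3.1.

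The oral-period row raises a smaller question of attribution. A value recorded before any study lurasidone can put a subject into a category presented as an oral-period finding. This applies to the absolute QTc categories as well as to the change categories.

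**Working it through.** The plan gives no figure on this point to reproduce. The check applies the text to the schedule and then sizes the oral-period effect.

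**1. Which ECG each sentence selects.** Let T be the clock time of injection.

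- First sentence (before the injection date): the last scheduled ECG is Day -6, 2 h after the tablet, whatever T is.
- Second sentence, read as the latest value on the injection date: the 12 h ECG falls on that date if T + 12 < 24, so T before 12:00. The 6 h ECG does if T + 6 < 24, so T before 18:00. The sentence therefore gives 12 h for T before 12:00, 6 h from 12:00 to before 18:00, and predose from 18:00.
- Date-and-time rule (last value before the injection): Day 1 predose at every T.

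These cut-offs assume nominal times and non-missing postdose ECGs. The ±15 minute window moves the 18:00 boundary to between about 17:45 and 18:15. If both postdose ECGs are missing, the second sentence reaches predose at any T. The documents do not state T. Lunch at least 4 h after dosing on Day 1 suggests an injection in the morning or around midday, but that is an inference.

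**2. How many changes would be affected under the literal reading.** Scheduled post-injection ECGs: 2 (Day 1) + 7 (Days 3 to 15) + 3 (Days 22, 29, 33) + 1 (follow-up) = 13.

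- 12 h ECG as baseline: 1 change is zero by construction, 1 (the 6 h ECG) precedes its own baseline, and 11 are measured from a value other than predose. Of those 11, 7 + 3 = 10 are time-matched, exactly or approximately, to Day 1 predose.
- Day -6 2 h ECG as baseline: all 13 are measured from a value other than predose.

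The documents give no basis for a shift in msec, so none is claimed.

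**3. Size of the oral-period effect.** The row holds 5 scheduled ECGs: Day -7 predose and 2 h, Day -6 predose and 2 h, and Day 1 predose. Without Day -7 predose it holds 4.

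Assumptions not in the documents: independent normal QTcF values, no drug effect, within-subject SD σ of 6 to 15 msec, and Day 1 predose as baseline. With k oral-period ECGs other than Day 1 predose, the probability of at least one increase above d is

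P(k) = 1 − ∫ Φ(z + d/σ)^k φ(z) dz.

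Now k = 4; after the fix k = 3. P(4) − P(3) is the probability of a flag due to Day -7 predose alone. For d = 30 msec (differences taken before rounding):

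| σ (msec) | P(4), % | P(3), % | Day -7 predose only, % | × 40 subjects |
|---|---|---|---|---|
| 6 | 0.078 | 0.059 | 0.019 | 0.01 |
| 8 | 1.414 | 1.100 | 0.313 | 0.13 |
| 10 | 5.469 | 4.363 | 1.106 | 0.44 |
| 12 | 11.475 | 9.349 | 2.126 | 0.85 |
| 15 | 21.216 | 17.721 | 3.495 | 1.40 |

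Forty is the planned maximum of five cohorts of 8; the counts shrink in proportion if fewer cohorts run. For d = 60 msec and σ = 15 the last column is 0.191% × 40 = 0.08. P(3)/P(4) runs from 0.76 to about 0.84, so most chance flags remain after the fix. It removes only those that cannot reflect study drug.

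No count is offered for the absolute QTc categories, because it would need the population distribution of QTcF. Protocol 7.2 excludes QTcF above 450 msec on the screening ECG only, so a pre-tablet Day -7 value above 450 msec remains possible and would be counted.

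**The case against.** The strongest reply is that the documents already settle the baseline. Protocol 14.3.9 names Day 1 predose and SAP 4.7 declares no departure. SAP 18.3 groups Day 1 predose with Baseline and assigns the Day 1 postdose timepoints to the injection period, so a 6 h or 12 h ECG cannot be baseline under that allocation. SAP 7.2 yields to more specific text. Its two sentences can be read together, the second being there to readmit a same-day predose value. All of this stands. A reader might infer that ECG changes will be computed from a post-injection value; the documents do not support that. They show wording that fails to say what was meant, made worse by the term pre-baseline, which may or may not mean baseline.

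Three other stronger readings also go too far.

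- One could take Protocol 11.3 as proof that the cut-off in SAP 7.3 is the tablet, because it records pretreatment events "until just prior to first lurasidone oral tablet study drug dose at Day -7". But its next sentence places the first study drug dose on Day 1, and SAP usage leans towards the injection. The term is unclear, and it governs unscheduled values only.
- One could conclude that the QTcF change criterion for dose escalation in Protocol 9.3 is compromised. The documents do not say that the Safety Review Team applies SAP 7.2.
- One could treat the 12:00 and 18:00 cut-offs as facts about this trial. They are conditional on an unstated injection time.

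On the oral-period row, the reply is that the table is descriptive, SAP 18 plans no group comparisons, and the by-timepoint rows still show Day -7 predose separately. That limits the consequence, but the row still counts a recording made before any study lurasidone.

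**Conclusion.** The point holds as a minor drafting defect in two places.

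First, SAP 7.2 read literally does not reliably select the Day 1 predose ECG, and this is an undeclared conflict with Protocol 14.3.9. The conclusion rests on the text and the ECG schedule; which wrong recording the same-day sentence selects depends on injection time and on the postdose ECGs being present. The intent is recoverable, so the finding is a risk of misprogramming, not evidence of it.

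Second, the overall oral-period row counts the pre-tablet Day -7 ECG in both the change-from-baseline and the absolute QTc categories. A reader might suppose the visit list is harmless for the absolute categories because they need no baseline. It is not, since a pre-tablet value above a threshold is counted there too. The effect is small: at most about 1.4 of 40 subjects for increases above 30 msec within the assumed SD range, and every such count depends on that assumption.

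**What to change.** - SAP 7.2: define baseline as the last non-missing value with a date and time before the injection (Day 1 predose as scheduled), state that this applies to ECG, and remove the term pre-baseline.
- SAP 7.3: make the injection the cut-off for unscheduled values, in place of the first dose of study medication.
- SAP 18.3: start the overall oral-period row after the first tablet for all ECG categories, which excludes Day -7 predose. Drop the duplicate Baseline record from that row. Leave the by-timepoint rows unchanged.

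The cost is three small edits to SAP wording and one derivation flag. No new data, new analysis or protocol change is needed. A separate pre-tablet baseline for the oral period is a different choice; it is not needed to cure this defect and would have to be declared in SAP 4.7.
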